5.4. Justification for Dose

The dosage of QWO (CCH-aaes) selected for this study for the control side is the labeled dose or lower. The labeled dose of 1.68 mg (0.84 mg per region) for a single treatment session and cumulative dose of 5.04 mg (after 3 treatment sessions each 21 days apart) when used at a concentration of 0.23 mg/mL have been shown to be safe and well-tolerated.

For Cohorts 1 and 5, half the labeled dose (0.42 mg per investigational side) will be administered to determine if the dose is associated with the severity of bruising. A similar dose was implemented in Study AUX-CC-831, a dose ranging study, where improvements were also observed in cellulite appearance at a dose of 0.48 mg per treatment region. The total cumulative dose in the investigational side and the control side for the participants allocated to these cohorts will be QWO (CCH-aaes) 3.78 mg (after 3 treatment sessions each 21 days apart).

For Cohort 6, half the labeled dose (0.42 mg for the control side) and one-quarter of the labeled dose at one-half the labeled concentration (0.21 mg at a concentration of 0.12 mg/mL for the investigational side) will be administered as 2 treatment sessions, 6 weeks apart. This is to determine whether a decrease in the dose and concentration combined with lengthening the time between treatment administration will decrease bruising and subsequent discoloration (refer to Section 5.2 for additional information).

For Cohort 7a and 7b, the labeled dose of QWO (CCH-aaes) will be administered. This is the first company sponsored study of tranexamic acid use to reduce bleeding due to QWO (CCH-aaes) which is 1300 mg TID for 5 days. Tranexamic acid will be taken during a single treatment session to help evaluate the potential effect in reducing bruising during QWO administration. Tranexamic acid will only be given during the first treatment session for the investigational buttock. The systemic effects are not expected to persist into the subsequent treatment visit.

5.5. End of Study Definition

A participant is considered to have completed the study if the participant has completed the Day 180 visit.

The end of the study is defined as the completion of the final assessment (Day 180) for the last participant enrolled in the study.

6. SELECTION AND WITHDRAWAL OF PARTICIPANTS

6.1. Participant Inclusion Criteria

Diagnosis and Inclusion Criteria

To be eligible to participate in the study, at the Screening Visit and on Day 1, participants must:

Age and Sex

1. Be female ≥ 18 and ≤ 60 years of age at the time of consent.

Disease Characteristics

- 2. Have a body mass index (BMI) of 18 to $< 32 \text{ kg/m}^2$ and intends to maintain stable body weight during the study (a variation of $\le 10\%$ from baseline body weight is permitted).
- 3. Have both buttocks with a score of 3 or 4 (moderate or severe cellulite) as reported by the investigator using the CR-PCSS.
- 4. Have a Hexsel Cellulite Severity Scale (CSS) Total Score of ≤ 12 .
- 5. Has a Fitzpatrick Skin Type of I-IV.

Type of Participant

6. Cohort 1 to 6: Be of nonchildbearing potential (history of hysterectomy, bilateral oophorectomy, bilateral tubal ligation, or postmenopausal with no history of menstrual flow in the 12 months prior to the Screening Visit); or, if of childbearing potential, be

nonpregnant, nonlactating and agree to use effective contraception when with a male partner for the duration of the study and for 28 days after any active treatment period. Acceptable forms of contraception include hormonal measures (oral contraceptive pills, contraceptive patch, contraceptive ring, and injections), intrauterine devices, double barrier method (condom plus diaphragm, condom or diaphragm plus spermicidal gel or foam), surgical sterilization of the male partner, and abstinence. Cohort 7: Combination hormonal contraceptives cannot be used.

- 7. Be willing and able to comply with all protocol required visits and assessments, including photography.
- 8. Be willing to apply sunscreen to the treatment areas before each exposure to the sun for the duration of the study (from the Screening Visit through the Day 180/Early Termination [ET] Visit).
- 9. Be willing to avoid the use of tanning beds, tanning booths or tanning lamps as well as outdoor tanning for the duration of the study (from the Screening Visit through the Day 180/Early Termination Visit).
- 10. Be a non-employee or non-family member of the sponsor or research staff conducting the study.

Informed Consent

11. Be adequately informed and understand the nature and risks of the study and be able to provide consent.

6.2. Participant Exclusion Criteria

A participant will be excluded from study participation if the participant:

Medical Conditions

- 1. Has any of the following systemic conditions:
 - a. Coagulation disorder including but not limited to a Factor II, V, VII, or X deficiency.
 - b. Skin pigmentation disorder.
 - c. Evidence or history of malignancy (other than excised basal-cell carcinoma) unless there has been no recurrence in at least 5 years.
 - d. History of keloid scarring or abnormal wound healing.
 - e. Concurrent diseases or conditions that might interfere with the conduct of the study, confound the interpretation of the study results, or endanger the participant's well-being, including but not limited to rheumatoid arthritis and/or other rheumatoid disease(s), Vitamin K deficiency, or liver diseases. Any questions about concurrent diseases should be discussed with the Medical Monitor.
 - f. Evidence of clinically significant abnormalities on physical examination or vital signs.
- 2. Is pregnant and/or is breast-feeding or plans to become pregnant and/or to breast-feed during the course of the study.

- 3. Has any of the following local conditions in the areas to be treated:
 - a. History of lower extremity thrombosis or post-thrombosis syndrome.
 - b. A current vascular disorder (eg, vasculitis, varicose veins, telangiectasia).
 - c. Inflammation or active infection (including lesions that indicate an active infection).
 - d. Active cutaneous alteration including, but not limited to, rash, eczema or psoriasis.
 - e. A tattoo or other artificially inflicted body marker in the treatment area.
 - f. A mole located within 2 cm of any injection site.

Prior/Concomitant Therapy

- 4. Requires the following concomitant medications during the study and cannot discontinue these medications within the time specified before QWO (CCH-aaes) treatment:
 - a. Antiplatelet medication, such as (clopidogrel [Plavix®], including aspirin) at any dose within 14 days of treatment.
 - b. Anticoagulants, such as warfarin (Coumadin®); heparin analogues, or Factor Xa inhibitors, within 14 days of treatment.
 - c. Non-steroidal anti-inflammatory drugs (NSAIDs), such as ibuprofen (Motrin®, Advil®) and naproxen (Aleve®) 7 days before the study.
 - d. Any medications (eg, corticosteroids, certain antidepressants [eg, citalopram, fluoxetine], nutritional/homeopathic supplements [eg, fish oil, Vitamin E, omega 3, gingko biloba, ginger, St John's Wort, green tea, ginseng, feverfew, saw palmetto, turmeric, bromelain]) or foods (eg, pineapple) that have, or have been reported to have anticoagulant effects within 14 days of treatment.
 - e. Has received treatment with tranexamic acid within 30 days before treatment.
- 5. Has used any of the following for the treatment of cellulite on either buttock within the specified timelines, or intends to use any of the following at any time during the study:
 - a. Liposuction during the 12-month period before dosing with study intervention.
 - b. Injections (eg, mesotherapy, dermal fillers, biostimulatory fillers); radiofrequency device treatments; laser treatment; buttock implant treatment; cryolipolysis or surgery (including subcision and/or powered subcision) during the 12-month period before injection of study intervention.
 - c. Any investigational treatment for cellulite during the 12-month period before the injection of study intervention.
 - d. Endermologie or similar treatments during the 6-month period before injection of study intervention.
 - e. Creams (eg, Celluvera[™], TriLastin[®]) and/or home therapies to prevent or mitigate cellulite during the 2-week period before injection of study intervention.
- 6. Intends to initiate an intensive sport or exercise program during the study.
- 7. Intends to initiate an intensive weight reduction program during the study.
- 8. Intends to engage in strenuous activity within 48 hours of study intervention administration.

- 9. Has recently tanned or intends to tan (outdoors or indoors). This includes, but is not limited to, the use of any tanning products or tanning booths/beds/lamps during the study.
- 10. Has a history of hypersensitivity or allergy to collagenase or any other excipient of CCH.
- 11. For Cohort 5: has a known history of hypersensitivity to local anesthetics of the amide type or a history of hypersensitivity to epinephrine.
- 12. For Cohort 5: are concurrently receiving to certain drugs like nitrites, antibiotics, or anticonvulsants, or any other drug which increases the risk of methemoglobinemia.
- 13. Has any condition(s) that, in the investigator's opinion, might indicate the participant to be unsuitable for the study.

Prior/Concurrent Clinical Study Experience

- 14. Has participated in a previous investigational study of CCH (EN3835, QWO [CCH-aaes]) or received any collagenase treatments at any time prior to treatment in this study for the treatment of cellulite of the buttocks.
- 15. Has received treatment with any investigational product within 30 days (or 5 half-lives, whichever is longer) of the start of the Screening Visit or throughout the study.

Additional Exclusion Criteria for Cohort 7

In addition to the applicable aforementioned exclusion criteria, participants enrolling in Cohort 7 will be excluded from study participation if the participant:

Medical Conditions

- 16. Has any of the following medical conditions:
 - a. history of venous or arterial thromboembolism or current thromboembolic disease.
 - b. history of or current renal impairment.
 - c. serum creatinine concentration > 1.4 mg/dL at Screening.

Prior/Concomitant Therapy

- 17. Requires the following concomitant medications during the study and cannot discontinue these medications within the time specified before QWO (CCH-aaes) treatment:
 - a. concurrently taking combination hormonal contraceptives.
 - b. concurrently undergoing hormone replacement therapy.
 - c. has a known history of hypersensitivity to tranexamic acid.
 - d. is a current smoker of nicotine or cannabinoids.

6.3. Lifestyle Considerations

Participants will be instructed to refrain from strenuous exercise for 48 hours after each treatment with QWO (CCH-aaes) and will be instructed to not initiate intensive sports, exercise, or weight reduction programs during the study.

Participants should avoid medications, homeopathic supplements, or foods as advised by the qualified designated physician or designee prior to QWO (CCH-aaes) treatment.

Participants should not use any tanning booth/beds/lamps, or tanning products during the study.

Participants in Cohort 7 should avoid smoking (including vaping, nicotine, or marijuana cigarettes) during the study.

6.4. Screen Failures

Screening procedures will be conducted during the Screening Period (Day -28 to Day -1).

Participants who do not meet all of the eligibility criteria will be deemed a screen failure and the following information must be recorded for all participants who are screen failures:

- Demography (age, gender, race/ethnicity).
- Reason for screen failure.
- Which eligibility criterion was not met.
- Any AEs (including SAEs) experienced by the participant.

No participant can be rescreened during this study.

7. STUDY INTERVENTION

Study intervention comprises QWO (CCH-aaes) and different doses, different concentrations, and different methods of administration of QWO (CCH-aaes) including diluent additives designed to decrease bruising.

7.1. Selection and Marking of Dimples

To ensure that the non-interventional buttock can serve as a control, and that a similar level of injection site bruising may be expected, participants should have a similar number of dimples requiring treatment on each buttock. Participants in Cohorts 1, 2, 3, 5, and 6 can be treated with up to 12 injections of QWO (CCH-aaes) on each buttock. The number of injections of QWO (CCH-aaes) administered to the right and left buttocks should be identical on Day 1. The number of injections may differ following the first treatment session, eg, 12 injections in each buttock in the first treatment session followed by fewer injections per buttock at the second and third treatment sessions as dimples improve.

Participants in Cohort 7 can be treated with up to 12 injections of QWO (CCH-aaes) on each buttock. Dimples will only need to be marked on the days of treatment. In Cohort 7a, on Day 1 only, the investigational buttock will be treated with QWO (CCH-aaes) and on Day 64 only the control buttock will be treated with QWO (CCH-aaes). On Days 22 and 43, both buttocks will be treated with QWO (CCH-aaes). In Cohort 7b, on Day 1, only the control buttock will be treated with QWO and on Day 64, only the investigational buttock will be treated with QWO (CCH-aaes). On Days 22 and 43, both buttocks will be treated with QWO (CCH-aaes).

For treatment, a qualified designated physician will select up to 12 dimples within each treatment area (each buttock) that are well-defined, evident when the participant is standing, and suitable for treatment.

For each dimple selected for treatment, a qualified designated physician will choose injection sites (injection sites within a dimple should be spaced approximately 2 cm apart, if a dimple requires more than 1 injection; locating at least 1 injection site at the nadir, if present, of the dimple). Each injection site will be marked with a "dot" using a surgical marker. For round dimples, the "dot" will be placed in the center of the dimple; for elongated dimples, "dots" will be spaced out approximately 2 cm along the longer axis of the dimple. The qualified designated physician will then use a surgical marker to circle each of the dimples selected for treatment.

In Cohort 4, the investigational side will receive QWO (CCH-aaes) at a labeled dose (0.84 mg) using a 2.5-fold diluted concentration (0.09 mg/mL) for up to 30 injections. The investigator will adapt an injection site stencil, which will be transferred to the location of injection. The number of injections will be adjusted by the clinician to best address the clinical presentation and need for treatment. QWO (CCH-aaes) will be administered as a single aliquot at a ¼-inch depth per injection. The control side will receive QWO (CCH-aaes) at the labeled dose (0.84 mg/treatment area) and concentration (0.23 mg/mL) but administering only a single aliquot at ¼-inch depth per injection administered as 12 injections.

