Bruising will be observed throughout the study. In an effort to standardize the risk and scope of bruising, the investigational and control sides in Cohorts 1 and 5 should be treated with the same concentration, same number of injections, and same number of aliquots per injection, but at different doses per injection or addition of diluent additive. In Cohort 2, the investigational and control sides will be treated with the same dose and number of injections, but the concentrations will vary. In Cohort 3, the investigational and control sides will be treated with the same dose, aliquots per injection, and number of injections, but at different injection depths. In Cohort 4, the dose will remain consistent between buttocks, but the number of injections and concentration will vary between the investigational and control sides. In Cohort 6, the investigational and control sides will be treated with the same number of injections, the same number of aliquots per injection, and an extended treatment interval, but at different doses and concentrations. In Cohort 7, the investigational and control sides should be treated with the labeled dose, injection technique and concentration of QWO (CCH-aaes) during each treatment visit, but oral tranexamic acid will be given before and after the first treatment with QWO (CCH-aaes) for the investigational buttock.

Participants will return to the site for 4 follow-up visits (1 to 2 days, 3 to 5 days, 6 to 9 days, and 10 to 14 days) after each treatment of QWO (CCH-aaes), for additional evaluations and digital photography to monitor the severity of bruising. Digital photographs will be obtained using a standardized method at each visit throughout the study. The effect of the different QWO (CCH-aaes) doses, strengths (concentrations), diluent additives, depths of injection, and methods of injection on the severity of bruising will be assessed by the investigator using the IABSS. The investigators will be evaluating the left (investigational) and right (control) buttocks separately with the IABSS. To assess the effect of QWO (CCH-aaes) on the severity of cellulite (efficacy), the investigator will complete the I-GAIS. Each buttock will be evaluated independently.

After completing the Treatment Period, participants will return for 3 follow-up visits at Days 90, 135, and 180 (EOS Visit).

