7.2. Treatment Administration

7.2.1. QWO (CCH-aaes)

QWO (CCH-aaes) and the other study interventions to potentially decrease bruising will be provided by Endo. The dose and volume of QWO (CCH-aaes) and other study interventions are detailed in Table 2. The dose of transamic acid is provided in Table 3.

 Table 2:
 Study Intervention (CCH-aaes) by Buttock

Cohort and Treatment Area	Dose per Each Injection	Injection Volume per Each Injection	Number of Injections at Each Treatment Visit	Dose (mg) at Each Treatment Visit	Injection Volume (mL) per Each Treatment Visit	Concentration (mg/mL)
Cohort 1 Right Buttock (control side)	CCH-aaes 0.07 mg	0.3 mL (given as three 0.1 mL aliquots)	Up to 12	Up to 0.84 mg	Up to 3.6 mL	0.23 mg/mL
Cohort 1 Left Buttock (investigational side)	CCH-aaes 0.035 mg	0.15 mL (given as three 0.05 mL aliquots)	Up to 12	Up to 0.42 mg	Up to 1.8 mL	0.23 mg/mL
Cohort 2 Right Buttock (control side)	CCH-aaes 0.07 mg	0.3 mL (given as three 0.1 mL aliquots)	Up to 12	Up to 0.84 mg	Up to 3.6 mL	0.23 mg/mL
Cohort 2 Left Buttock (investigational side)	CCH-aaes 0.07 mg	1.5 mL (given as three 0.5 mL aliquots)	Up to 12	Up to 0.84 mg	Up to 18 mL	0.05 mg/mL
Cohort 3 Right Buttock (control side)	CCH-aaes 0.07 mg	0.3 mL (given as three 0.1 mL aliquots)	Up to 12	Up to 0.84 mg	Up to 3.6 mL	0.23 mg/mL
Cohort 3 Left Buttock (investigational side)	CCH-aaes 0.07 mg	0.3 mL (given as three 0.1 mL aliquots)	Up to 12	Up to 0.84 mg	Up to 3.6 mL	0.23 mg/mL
Cohort 4 Right Buttock (control side)	CCH-aaes 0.07 mg	0.3 mL (given as one 0.3 mL aliquot)	Up to 12	Up to 0.84 mg	Up to 3.6 mL	0.23 mg/mL
Cohort 4 Left Buttock (investigational side)	CCH-aaes 0.028 mg	0.3 mL (given as one 0.3 mL aliquot)	Up to 30	Up to 0.84 mg	Up to 9 ml	0.09 mg/mL
Cohort 5 Right Buttock (control side)	CCH-aaes 0.07 mg	0.3 mL (given as three 0.1 mL aliquots)	Up to 12	Up to 0.84 mg	Up to 3.6 mL	0.23 mg/mL
Cohort 5 Left Buttock	CCH-aaes 0.035 mg	0.15 mL (given as three 0.05 mL	Up to 12	Up to 0.42 mg	Up to 1.8 mL	0.23 mg/mL
(investigational side)	Lidocaine 2% and Epinephrine 1:200,000	aliquots)		36 mg Lidocaine 9 mcg Epinephrine		Lidocaine 20 mg/mL Epinephrine 5 mcg/mL
Cohort 6 Right Buttock (control side)	CCH-aaes 0.035 mg	0.15 mL (given as three 0.05 mL aliquots)	Up to 12	Up to 0.42 mg	Up to 1.8 mL	0.23 mg/mL
Cohort 6 Left Buttock (investigational side)	CCH-aaes 0.018 mg	0.15 mL (given as three 0.05 mL aliquots)	Up to 12	Up to 0.21 mg	Up to 1.8 mL	0.12 mg/mL

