7.2.2. Cohorts 1-5, Control Sides, QWO (CCH-aaes) – Labeled Dose and Concentration

Dosage and Mode of Administration: For the control side, a dose of up to 0.84 mg of QWO (CCH-aaes) up to 3.6 mL will be administered as up to 12 subcutaneous injections (0.3-mL injection administered as three 0.1-mL aliquots per injection with the exception of Cohort 4 in which a single 0.3 mL injection will be utilized) for a total dose of 1.68 mg. There will be 3 treatment visits at intervals of approximately 21 days as described in schedule of assessments. All injections will be given at the labeled depth of ½ inch, except in Cohort 3 and 4, where injections will be given at a depth of ½ inch.

To induce a similar extent and severity of bruising in each buttock, approximately the same number of injections should be administered to the left and to the right buttock. However, the

^b The control side will be treated with QWO (CCH-aaes) on Days 22, 43, and 64.

^c The investigational side will be treated with QWO (CCH-aaes) on Days 22, 43, and 64.

^d The control side will be treated with QWO (CCH-aaes) on Days 1, 22, and 43.

number of injections per buttock may differ among treatments. The number of injections administered to each buttock must be recorded. The volume and dose of injection at each treatment visit for each buttock will be prepared per the Pharmacy Manual and injected per the Injection Guide in the Study Operations Manual.

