Dosage and Mode of Administration: For the investigational side, a dose of up to 0.84 mg of QWO (CCH-aaes) up to 9 mL will be administered as up to 30 subcutaneous injections (0.3-mL injection administered as one 0.3-mL aliquot per injection at a depth of ½ inch) for a total dose of 1.68 mg. There will be 3 treatment visits at intervals of approximately 21 days as described in schedule of assessments. The volume and dose of injection at each treatment visit for each buttock will be prepared per the Pharmacy Manual and injected per the Study Operations Manual.

7.2.7. Cohort 5, Investigational Side Only, QWO (CCH-aaes) – Half-dose at a Labeled Concentration with Lidocaine 2% and Epinephrine 1:200, 000 as a Diluent Additive

Dosage and Mode of Administration: For the investigational side, a dose of up to 0.42 mg of QWO (CCH-aaes) up to 1.8 mL will be administered as up to 12 subcutaneous injections (0.15-mL injection administered as three 0.05-mL aliquots per injection). There will be 3 treatment visits at intervals of approximately 21 days as described in the Schedule of Assessments. The volume and dose of injection at each treatment visit for each buttock will be prepared per the Pharmacy Manual and injected per the Injection Guide in the Study Operations Manual. QWO (CCH-aaes).

7.2.8. Cohort 6, Investigational Side Only, QWO (CCH-aaes) – Quarter-dose with One-Half Concentration and Two Treatment Sessions at Approximately 42 Days Between Visits

Dosage and Mode of Administration: For the investigational side, a dose of up to 0.21 mg of QWO (CCH-aaes) up to 1.8 mL will be administered as up to 12 subcutaneous injections (0.15-mL injection administered as three 0.05-mL aliquots per injection). Half the standard concentration (0.12 mg/mL) will be used.

There will be 2 treatment visits at an interval of approximately 42 days as described in Schedule of Assessments for Cohort 6. The volume and dose of injection at each treatment visit for each buttock will be prepared per the Pharmacy Manual and injected per the Injection Guide in the Study Operations Manual.

7.2.9. Cohort 6, Control Side Only, QWO (CCH-aaes) – Half of the Labeled Dose (0.42 mg/control side) Using the Labeled Concentration (0.23 mg/mL) at Approximately 42 Days between Visits

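### In Cohort 4 the injection-count instructions conflict and none secures the equal dose stated in Protocol 5.1, so Day 1 doses can differ between sides in the Visit 3 primary

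*Protocol*

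**What the plan says.** **Equal dose.** Protocol 5.1 states: "In Cohort 4, the dose will remain consistent between buttocks, but the number of injections and concentration will vary" between the two sides. Section 3.3.5 rests its benefit-risk statement for the diluted concentrations on the same 0.84 mg being given.

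**Dose per injection.** For the Cohort 4 left side, Table 2 gives "CCH-aaes 0.028 mg" in 0.3 mL, up to 30 injections. For the right side it gives 0.07 mg in 0.3 mL, up to 12 injections. Each side is capped at 0.84 mg.

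**Injection counts.** Four places bear on how many injections a Cohort 4 participant gets:

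- Section 7.1, Cohort 4 text: the left side has up to 30, and "The number of injections will be adjusted by the clinician to best address the clinical presentation and need for treatment". The right side is a single aliquot at ¼-inch "depth per injection administered as 12 injections". Table 1, Table 2 and 7.2.2 all say up to 12.
- Section 7.1, opening paragraph: counts "administered to the right and left buttocks should be identical on Day 1". That sentence follows a list of Cohorts 1, 2, 3, 5 and 6, which omits Cohort 4.
- Section 7.2.2, headed for Cohorts 1-5: approximately the same "number of injections should be administered to the left and to the right buttock". The section does carve out Cohort 4 for aliquots ("with the exception of Cohort 4 in which a single 0.3 mL injection will be utilized") and for depth, but not for count.
- Section 7.2.6: the left-side dose "will be administered as up to 30 subcutaneous injections", with no reference to the right-side count.

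**Analysis.** SAP 7.6.1.1 summarises the Visit 3 responder proportion by cohort with a Clopper-Pearson interval and lists no supportive analysis. SAP 7.7.1 tabulates injection count and dose by visit, cohort and side.

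**The concern.** The Cohort 4 primary is read three to five days after the Day 1 session, so whatever differs between sides on Day 1 goes into it. Concentration, puncture count and volume differ by declared design. Dose is the one quantity that 5.1 says is held equal, yet a clinician can follow 7.1 or 7.2.2 to the letter and give unequal doses.

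The sponsor regards dose as a plausible driver of bruising: Cohort 1 tests 0.42 mg against 0.84 mg for that reason. A Cohort 4 participant given 15 left and 12 right injections receives those same two doses. If that happened often, the Cohort 4 result would contain a dose contrast that the protocol says is absent, and 5.2 describes the study as an attempt to isolate each variable.

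**Working it through.** **Inputs (Protocol Table 2, Cohort 4).** Left 0.028 mg per injection, maximum 30. Right 0.07 mg per injection, maximum 12. Both 0.3 mL per injection.

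**Reproducing the plan's figure.** Dose = count × dose per injection.

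- Left: 30 × 0.028 = 0.84 mg. Right: 12 × 0.07 = 0.84 mg. Both agree with Table 2.
- Volume: 30 × 0.3 = 9 mL and 12 × 0.3 = 3.6 mL. Both agree.
- Using the rounded concentrations instead: 30 × 0.3 × 0.09 = 0.81 mg and 12 × 0.3 × 0.23 = 0.83 mg. The gap is rounding only.

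**Count ratio needed for equal dose.** Left count × 0.028 = right count × 0.07, so left/right = 0.07 / 0.028 = 2.5. That gives 30/12, 25/10 and 20/8.

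**Doses at other permitted counts.**

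| Left / right count | Left mg | Right mg | Left/right dose |
|---|---|---|---|
| 30 / 12 | 0.840 | 0.84 | 1.00 |
| 24 / 12 | 0.672 | 0.84 | 0.80 |
| 20 / 12 | 0.560 | 0.84 | 0.67 |
| 15 / 12 | 0.420 | 0.84 | 0.50 |
| 12 / 12 | 0.336 | 0.84 | 0.40 |
| 25 / 10 | 0.700 | 0.70 | 1.00 |
| 30 / 10 | 0.840 | 0.70 | 1.20 |
| 30 / 8 | 0.840 | 0.56 | 1.50 |

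The 12/12 row is what the 7.2.2 sentence produces if applied to Cohort 4. The last two rows need a right count below 12, which Table 1, Table 2 and 7.2.2 allow and 7.1 does not. These are values within the permitted range; the documents give no actual counts.

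**Whether a whole-number rule works.** With an odd right count, 2.5 times is not whole. For 11 right, 27 left gives 0.756/0.77 = 0.98 and 28 gives 0.784/0.77 = 1.02. For 3 right, 7 left gives 0.196/0.21 = 0.93 and 8 gives 0.224/0.21 = 1.07. Rounding therefore keeps the ratio within 0.90-1.10 for any right count of 2 or more.

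**The case against.** **The protocol does link the two counts.** A reader might infer that nothing ties left to right. The documents do not support that: 5.1 with Table 2 implies 2.5:1, 7.2.2 states a link (a different one), and Section 9 requires adherence to the design and bars waivers. On this view a 15/12 session already breaches 5.1. That stands as far as it goes. But the ratio has to be worked out by division, while the sections a clinician uses on the day say something else.

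**The 12/12 case is a strained reading.** The 7.2.2 sentence is general, sits under a control-side heading, and conflicts with Cohort 4 text allowing up to 30 left injections. It is probably not how sites would proceed. Still, the section makes two Cohort 4 exceptions and omits this one.

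**The direction is not fixed.** A reader might infer that any departure lowers the left dose and so favours the investigational side. That requires the right side to be fixed at 12, which only 7.1 says. With up to 12, the ratio can exceed 1. Section 7.1 also asks for similar numbers of dimples on each buttock, so a low left need would usually come with a low right need.

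**Dilution is not isolated anyway.** At equal dose the sides still differ in punctures (30 against 12) and volume (9 against 3.6 mL). This stands in full. A lower left count changes dose, punctures and volume together, so a shift in responders could not be credited to dose alone. The other differences are declared, however; a dose difference contradicts 5.1.

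**Mitigation exists.** The Study Operations Manual, which is not available here, may hold a count rule with the stencil. The SAP exposure table and listings would show an imbalance afterwards. The endpoint is descriptive. These points lower the stakes but do not reconcile the protocol sections.

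**Conclusion.** The point holds as a conflict between protocol sections with a route into the Cohort 4 primary. None of the count instructions secures the stated equal dose. Counts within the stated limits give left/right ratios such as 0.40, 0.50, 1.20 and 1.50 against the intended 1.00.

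The effect on the responder proportion is unknown in size and direction. The documents give no Cohort 4 counts, no distribution of bruising scores and no dose-bruising slope. The nearest evidence, in 3.3.3, is that bruising and discoloration were slightly less frequent numerically at 0.48 mg than at 0.84 mg, in a study that did not compare severity between doses. Any figure for added responders would rest on assumed inputs.

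A reader might also infer that restoring equal dose would make Cohort 4 a clean test of dilution. It would not, because puncture count and volume still differ by design. The primaries of the other cohorts are unaffected. The conclusion assumes that no unseen manual already fixes the ratio and that sites do not simply use 30/12 for everyone. The correction should be made, given how little it costs.

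**What to change.** 1. In 7.1 (Cohort 4 text) and 7.2.6, state that on Day 1 the left count is 2.5 times the right count, rounded to a whole injection: 30/12, 25/10, 20/8. This plays the part that the identical-count sentence plays for the other cohorts in 7.1.
2. In 7.1, change the right-side count from 12 to up to 12, to match Tables 1 and 2.
3. In 7.2.2, limit the same-number sentence to Cohorts 1, 2, 3 and 5.

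The cost is three short edits and less clinician freedom over the left count on Day 1. Later sessions can stay flexible.

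If Cohort 4 has already been dosed, an optional SAP addition is to report the Day 1 left/right dose ratio beside the Cohort 4 primary, with the responder proportion among participants near a ratio of 1 (0.90-1.10 is a workable but arbitrary band). Counts per buttock are already recorded. This should be labelled descriptive and imprecise: the subset is selected by clinician choice, and at 50% responders the Clopper-Pearson interval is 31%-69% with 15 of 30 but 21%-79% with 6 of 12. The planned full-analysis-set proportion stays as it is.
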